	occurring > 3 months after index surgery.
	3. Patient Reported Outcomes (QoL and pain assessments).
	4. True hernia recurrence at the site of surgery at
	post-operative day 90 and months 12 and 24 months.
Clinic Visits	Baseline, hospital stay (admission, day of surgery, day of discharge),
	30 days, 90 days, 12 months, 24 months.

Time and Events Schedule

Assessments	Baseline Visit (BV)	Hospital Stay			Post-operative Visits			
		Admission	Day of Surgery (DOS)	Day of Discharge (DOD)	Day 30 (±2wks)	Day 90 (±2wks)	Month 12 (±4wks)	Month 24 (±4wks)
Informed Consent	X							
I/E Criteria	X		X					
Medical History	X		X					
Physical Exam	X		X					
Hospitalization & Perioperative Information		X	X	X				
Surgeon Assessment of Mesh			X					
Surgical Site Assessment *				X	X	X	X	X
Ventral Hernia Assessment	X**				X	X	X	X
Pain Visual Analogue Scale					X	X	X	X
QOL scales	X				X	X	X	X
Subject/Surgeon Satisfaction					X	X	X	X
Adverse Events			X	X	X	X	X	X

^{*} Surgical site assessment is intended to document any surgical site occurrences of wound related events noted at the hernia repair site.

^{**} Baseline ventral hernia assessment is intended to estimate the actual hernia defect size.

LIST OF TABLES

Table 1: Adverse Event Severity

LIST OF FIGURES

Figure 1: Image of OviTex 1S Permanent RBS

Investigational Plan OviTex®

Page 9

v2.0_15-Jun-2017

Glossary of Terms and Abbreviations

AE Adverse Event

ASA American Society of Anesthesiologists

BV Baseline Visit

BMI Body Mass Index

CFR Code of Federal Regulation

Cm Centimeter

COPD Congestive Obstructive Pulmonary Disorder CO2 Carbon Dioxide

CRF Case Report Form

CT Computerized Tomography

CV Curriculum Vitae
DOS Day of Surgery

EBL Estimated Blood Loss

ECM Extracellular Matrix

EQ-5D EuroQol 5 Dimension

FDA U.S. Food and Drug Administration

GAGs Glycosaminoglycans

GCP Good Clinical Practice

HerQLes Hernia-Related Quality-of-Life Survey to Assess Abdominal Wall Function

ICH International Conference on Harmonization

I/E Inclusion/Exclusion

IRB Institutional Review Board

ISO International Organization for Standardization

MEC Medical Events Committee

Mm Millimeter

OTC Over the Counter
OTM Ovine Tissue Matrix

OR Operating Room

PE Physical Exam

POD Post Operative Day(s)
PTFE Polytetrafluoroethylene

QoL Quality of Life

RBS Reinforced BioScaffold
SAE Serious Adverse Event
SSI Surgical Site Infection

UADE Unanticipated Adverse Device Effect

VAS Visual Analogue Scale

WKS Weeks

STUDY OVERVIEW

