2.2.2 Secondary Endpoints

- Incidence of late post-operative surgical site occurrences or wound related events (e.g. ileus, deep or superficial wound infection, seroma, hematoma, wound dehiscence, skin necrosis, fistulae, bulging) noted at the hernia repair site and occurring > 3 months after index surgery.
- 2. Incidence of other late post-operative complications (e.g. ileus, bowel obstruction, fistula) occurring > 3 months after index surgery.
- 3. Patient Reported Outcomes (QoL and pain assessments).
- 4. True hernia recurrence at the site of surgery at post-operative day 90 and 12 and 24 months.

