3.2.3 Discharge

On the day of hospital discharge, the following will be collected:

- Length of Stay, including number of days hospitalized prior to repair and following surgery, the number of days in ICU, step down and regular ward.
- Number of drains still in place, drain volume and duration.
- Any early surgical site occurrences (infections, seroma, hematoma, wound dehiscence)
 or wound related events noted at the hernia repair site.
- Any other early post-operative complications (ileus, fistulae).

3.3 POST-OPERATIVE DAYS 30 AND 90

At post-operative days 30 and 90, the following procedures will be completed:

- Number of drains still in place, drain volume and duration.
- Assessment of any surgical site occurrences or wound related events (infections, seromas, hematoma, wound dehiscence) noted at the hernia repair site.
- A relevant physical examination to evaluate hernia repair. If there is any suspicion of a recurrent hernia e.g. bulging noted at the repair site, an abdominal CT scan will be performed to confirm the clinical diagnosis. If it is determined that it is clinically necessary to repair the hernia recurrence during the study period, those subjects will complete their participation in the study at the time of that repair
- Assessment of any other post-operative complications (ileus, fistulae).
- Assessment of disease specific and general Quality of Life (QoL) surveys e.g. EQ-5D and HerQLes, (See Appendix 1).
- Subject and Surgeon satisfaction assessment of hernia repair (See Appendix 5).
- Subject assessment of post-operative pain as measured by the Pain Visual Analog Scale ((VAS) See Appendix 5).

3.4 POST-OPERATIVE MONTHS 12 AND 24

The following activities will be performed at months 12 and 24 of Study period visit:

- Assessment of any late surgical site occurrences or wound related events (e.g. infections, seromas, hematoma, wound dehiscence, bulging) noted at the hernia repair site.
- A relevant physical examination to evaluate hernia repair. If there is any suspicion of a recurrent hernia e.g. bulging noted at the repair site, an abdominal CT scan will be performed to confirm the clinical diagnosis. If it is determined that it is clinically necessary to repair the hernia recurrence during the study period, those subjects will complete their participation in the study at the time of that repair.

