• Assessment of any other late post-operative complications (e.g. ileus, fistulae). Assessment of disease specific and general Quality of Life (QoL) surveys e.g. EQ-5D and HerQLes, (See Appendix 1).

- Subject and Surgeon satisfaction assessment of hernia repair (See Appendix 4).
- Subject assessment of post-operative pain as measured by the Pain Visual Analog Scale ((VAS) See Appendix 5).

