5 PATIENT WITHDRAWAL AND LOST TO FOLLOW-UP

Subjects have the right to withdraw from the study at any time for any reason. Subjects who wish to withdraw from the study should be instructed to notify the investigator in writing. The Investigator, acting in the best interests of the patient, also has the right to withdraw subjects from the study.

If the reason for removal of a subject from the study is an adverse event, the event will be recorded on the Adverse Event Case Report Form. In the case of any Serious Adverse Event (SAE) or Unanticipated Device Effect (UADE) the Investigator is also required to report the event using the required reporting forms. All efforts will be made to follow-up the patient until the condition resolves or Investigator determines that the patient's health has returned to an acceptable state.

In the event that a patient is lost to follow-up (LTFU), the Investigators should document due diligence efforts to maintain contact with any subjects with at least 3 attempts by email or telephone with the final attempt being made by certified mail.

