7.2 STATISTICAL METHODS

Statistical methods will be carried out in accordance with the Statistical Analysis Plan (SAP) developed for this study.

The majority of data will be expressed as descriptive statistics. A p-value of less than or equal to 0.05 will be considered statistically significant. Any confidence bounds will show two-sided 95% confidence interval limits. Categorical variables will be summarized by number and percent. Continuous variables will be summarized by total number (N), mean, standard deviation, median, min and max. It is anticipated that the data will be evaluated using standard parametric and non-parametric procedures. Analyses of particular interest will be:

1. Correlation of rate of surgical site wound infection to SSI wound classification, number of previous repairs and pre-morbid conditions.

- 2. Correlation of surgical site occurrences or wound related events to re-herniation, BMI, number of previous abdominal.
- 3. Correlation of number of previous repairs with true hernia recurrence
- 4. Correlation of a visible bulge at hernia repair site with true hernia recurrence
- 5. Correlation of subject abdominal wall function and QoL with bulging at the hernia repair site and hernia recurrence rates.

The primary and secondary endpoints of this study will be also be compared to the clinical outcomes reported for other prospective studies in the literature. The results will be compared for the group as a whole, and, if the numbers will allow this, for subgroups of subjects exhibiting similar baseline characteristics, such as size of the hernia, co-morbid conditions, number of previous abdominal procedures etc.

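### Exit at recurrence repair without a pre-repair questionnaire leaves recurrences repaired between visits with no quality-of-life or pain score taken while the hernia was present

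*Combined protocol and SAP*

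**What the plan says.** Sections 3.3 and 3.4 carry the same exit rule. When a recurrence is judged clinically to need repair within the study period, the consequence is that "those subjects will complete their participation in the study at the time of that repair". A recurrence that is not repaired does not end participation.

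The Study Synopsis lists the post-operative clinic visits as "30 days, 90 days, 12 months, 24 months". In the Time and Events Schedule, the QOL scales, pain VAS and satisfaction form appear after surgery only in those four columns. There is no exit, early-termination or unscheduled-visit column. Section 5 opens with "Subjects have the right to withdraw from the study at any time for any reason" and covers withdrawal, follow-up of adverse events and loss to follow-up, but asks for no final questionnaire.

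The visits that examine the hernia repair also include "Assessment of disease specific and general Quality of Life (QoL) surveys e.g. EQ-5D and HerQLes" and "Subject assessment of post-operative pain as measured by the Pain Visual Analog Scale".

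These data feed two parts of the plan:
- Section 2.2.2, secondary endpoint 3: "Patient Reported Outcomes (QoL and pain assessments".
- Section 7.2, analysis of particular interest 5: "Correlation of subject abdominal wall function and QoL with bulging at the hernia repair site and hernia recurrence rates". The pain VAS is not named there.

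Section 7.2 refers statistical methods to an SAP whose text is not in the document supplied. Section 7.2 itself does not say which visit's score enters analysis 5, or how missing scores are handled.

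**The concern.** After Day 90 the visits are 9 and then 12 months apart. A subject may have an intact repair at Day 90, recur at month 6 and be re-operated at month 9. That subject leaves with a Day 90 questionnaire that predates the recurrence and with nothing later.

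The loss is informative, because it is the judgement that the recurrence needs repair that removes the subject. Recurrences that can be left alone stay in the study and keep contributing scores.

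Two results are exposed. Analysis 5 may understate how far recurrence is associated with poorer abdominal wall function and quality of life. The Month 12 and Month 24 quality-of-life and pain summaries for secondary endpoint 3, which Section 7.2 also intends to compare with the literature, say nothing about subjects already re-repaired. No later analysis can recover a form that was never given.

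**Working it through.** The plan has no figure to reproduce. Section 7.1 calls the 100 subjects a convenience sample, and nothing is stated about the share of recurrences repaired, the delay to repair or the expected scores. What follows is an illustration.

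**Step 1: how often a repaired recurrence has no score while present.** The visits at months 1, 3, 12 and 24 come from the Time and Events Schedule. Assumptions: repair follows onset by a fixed delay d, repair falls within 24 months, and onset is uniform over 0 to 24 − d. A recurrence with onset t has a score if a visit falls in [t, t + d]. The missed share is g = 1 − (length of onset times seen) / (24 − d).

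| d (months) | 24 − d | Onset times seen at a visit | g |
|---|---|---|---|
| 1 | 23 | 0–1, 2–3, 11–12: 3 | 20/23 = 87% |
| 3 | 21 | 0–3, 9–12: 6 | 15/21 = 71% |
| 6 | 18 | 0–3, 6–12: 9 | 9/18 = 50% |
| 9 | 15 | 0–12: 12 | 3/15 = 20% |
| 12 | 12 | 0–12: 12 | 0% |

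**Step 2: number of subjects.** Recurrences without such a score = R × f × g, where R is the number of recurrences per 100 subjects and f the share repaired. With R = 10, f = 50% and d = 3 (all assumed): 10 × 0.5 × 0.714 = 3.6 of 10. Section 1.1 cites recurrence rates from 2.7% to 62%. At those ends, with the same f and d, the numbers are 2.7 × 0.357 = 1.0 and 62 × 0.357 = 22.1 per 100 subjects.

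**Step 3: effect on analysis 5.** Assume mean scores of 80 without recurrence, 65 with an unrepaired recurrence and 45 just before repair, on a 0–100 scale where higher is better. The scale is itself an assumption: Appendix 1 shows 12 items scored 1 to 6 (raw maximum 72) and gives no scoring rule. The deficits from 80 are then 15 and 35. Assume also that recurrences with no score taken while present are left out. With k of R recurrences repaired:

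- Full difference = [(R − k) × 15 + k × 35] / R
- Observed difference = [(R − k) × 15 + k(1 − g) × 35] / [(R − k) + k(1 − g)]

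For R = 10 and k = 5, the full difference is (75 + 175)/10 = 25.

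| d | k(1 − g) | Observed difference | Recovered |
|---|---|---|---|
| 1 | 0.652 | 97.8/5.652 = 17.3 | 69% |
| 3 | 1.429 | 125/6.429 = 19.4 | 78% |
| 6 | 2.5 | 162.5/7.5 = 21.7 | 87% |
| 9 | 4 | 215/9 = 23.9 | 96% |
| 12 | 5 | 250/10 = 25.0 | 100% |

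For R = 15 and k = 10, the full difference is 425/15 = 28.3, and the recovered shares at 1, 3 and 6 months are 68%, 79% and 88%.

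**Step 4: mix of recurrences left in analysis 5.** The unrepaired share among recurrences with a usable score is (1 − f)/(1 − f × g), against 1 − f if none were lost. At f = 50% and d = 3 it is 0.5/0.643 = 78% instead of 50%. At f = 75% and d = 6 it is 0.25/0.625 = 40% instead of 25%.

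**The case against.** The strongest reply is that quality of life and pain are collected at every visit where the repair is examined, and that Section 2.2.2 sets recurrence at Day 90, Month 12 and Month 24, all of which have questionnaires. A recurrence found at one of those visits is fully scored before the subject exits. This stands, and it confines the point to recurrences that arise and are repaired between visits, plus the visits after exit.

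A reader might infer several stronger things that the documents do not support:

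- *That scores are missing for the worst recurrences, so that analysis 5 rests mostly on mild ones.* The exit rule speaks of clinical necessity, not of quality of life. Step 4 shows that unrepaired cases can remain a minority (40% at f = 75%, d = 6). With f = 25% they would be 75% even if no score were lost.
- *That analysis 5 would recover only 50–60% of the difference.* With unscored recurrences left out, this needs every repaired recurrence to be missed: 15/25 = 60% or 15/28.3 = 53%. None of the delays in Step 1 gives g = 100%.
- *That the Month 12 and Month 24 means are too favourable by a calculable amount.* That would carry a pre-repair score past a new repair. Nobody knows these subjects' later scores, and an exit form would not supply them.
- *That the recurrence count is biased.* Exit follows diagnosis, and Section 6.3.1 has recurrent hernia recorded as an adverse event.

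It is also fair to say that the SAP named in Section 7.2 may specify the score used in analysis 5, and that analysis 5 is one of five correlations in a mainly descriptive study. The first does not restore questionnaires that were never given. The second bears on severity.

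**Conclusion.** The point holds for recurrences that arise and are repaired between scheduled visits. For these the plan collects no HerQLes, EQ-5D or pain score while the recurrence is present, and because exit depends on the need for repair, the loss is informative. It may weaken the association in analysis 5, and it makes the Month 12 and Month 24 quality-of-life and pain summaries unrepresentative of these subjects. The missing pain scores concern secondary endpoint 3 only.

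The size depends on the delay to repair, which the documents do not give: from 87% of repaired recurrences unscored at 1 month to none at 12 months. Under the assumed scores, analysis 5 would recover about 69% of the difference at 1 month, 78% at 3, 87% at 6 and all of it at 12. Uniform onset, the repair share, the score values and the 0–100 scale are all assumptions. The recurrence count and the primary endpoints are not affected.

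Severity: minor. Label: cheap improvement.

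**What to change.** - Add a column 'Exit / before repair of recurrence' to the Time and Events Schedule with the existing QOL scales, pain VAS and satisfaction form. These are completed where feasible after the decision to repair and before the repair. Refer to the column in Sections 3.3 and 3.4. Whether and when a repair is done does not change, and participation can still end at the repair.
- State for analysis 5 that the score used for a subject with recurrence is one taken at or after diagnosis and before any repair. For subjects repaired between visits this is the exit score.
- Report exit scores separately, labelled with their time since surgery. Do not carry them forward as Month 12 or Month 24 values.
- Beside the Month 12 and Month 24 means, give the number of subjects who had exited for repair.

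The cost is one set of existing forms in a small number of subjects. Exit scores will fall at irregular times, and some repairs may be urgent or take place elsewhere and yield no form, so the gap will shrink but may not close.

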4 CONCOMITANT PROCEDURES/TREATMENTS AND ADVERSE EVENTS

All treatments, surgeries, procedures and Adverse Events will be recorded for the duration of the study. All AEs, UADEs and SAEs that occur from the day of surgery through the Month 24 visit will be reported in the CRF. In addition to notation in the CRF, all SAEs will also require completion of a separate reporting form for submission to the Sponsor through Day 90. Any Serious Adverse Events (SAEs) or Unanticipated Adverse Device Effects (UADEs) will be reported to TELA Bio (or their designee) within 24 hours of the investigator's first awareness of their occurrence. Following the Day 90 visit, only SAEs considered by the investigator to be "Related or "Possibly Related" to the study product will require completion of the additional reporting form for submission to the Sponsor. Conversely, following the Day 90 visit, it will no longer be necessary to complete the separate reporting form for those SAEs that the investigator determines to be "Unrelated" to the OviTex mesh.

5 PATIENT WITHDRAWAL AND LOST TO FOLLOW-UP

Subjects have the right to withdraw from the study at any time for any reason. Subjects who wish to withdraw from the study should be instructed to notify the investigator in writing. The Investigator, acting in the best interests of the patient, also has the right to withdraw subjects from the study.

If the reason for removal of a subject from the study is an adverse event, the event will be recorded on the Adverse Event Case Report Form. In the case of any Serious Adverse Event (SAE) or Unanticipated Device Effect (UADE) the Investigator is also required to report the event using the required reporting forms. All efforts will be made to follow-up the patient until the condition resolves or Investigator determines that the patient's health has returned to an acceptable state.

In the event that a patient is lost to follow-up (LTFU), the Investigators should document due diligence efforts to maintain contact with any subjects with at least 3 attempts by email or telephone with the final attempt being made by certified mail.

6 ADVERSE EVENTS

An adverse event is any unfavorable, unintended sign, symptom, condition or disease in a study subject, where the experience occurs during the course of the study, regardless of its relationship to the test product or surgical procedure. Follow-up of an AE, even after the completion of the study is required until the event or its sequelae resolve or stabilize at a level acceptable to the Investigator and TELA Bio.

All AEs will be recorded in the Electronic Case Report Form and source documents. The Investigator will assess each event in terms of severity and relationship to study product, as follows:

	TABLE 1				
Intensity	Definition				
Mild	Experiences that are transient, requiring no special treatment, or do not interfere with the subject's daily activities				
Moderate	Experiences that introduce some level of inconvenience or concern to the subject and may somewhat interfere with daily activities but are usually ameliorated by simple therapeutic measures, such as over the counter (OTC) medications.				

Severe	Experiences that are unacceptable or intolerable, significantly interrupt the subject's usual daily activity, and/or require systemic drug therapy or other treatment, including other medical or surgical intervention or hospitalization.
--------	---

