A baseline visit will be performed prior to the ventral hernia repair and will include assessment of the subject's medical history, physical exam and pre-operative instructions. The subjects will also complete baseline Quality of Life (QOL) Surveys, one of which will be a disease specific assessment (HerQLes) and the other a standard measure of health outcomes (EQ-5D)

On the day of surgery, repair of the ventral hernia will occur using OviTex® Permanent 1S reinforced bioscaffold to reinforce the repaired hernia site. Perioperative data will be collected, including the anatomical placement of the mesh and fixation methods. During the course of hospitalization the patient will be assessed for incidence of early post-operative surgical site wound events and complications including the nature and severity of the complications, all necessary medical interventions and/or re-operations.

On the day of hospital discharge, surgical site occurrences or wound related events (e.g. infections, hematomas, seromas, wound dehiscence) noted at the hernia repair site and the occurrence of other early post-operative complications (e.g. ileus, bowel obstruction, fistulae) will be assessed.

At post-operative days 30 and 90, surgical site occurrences or wound related events (e.g. infections, hematomas, seromas, wound dehiscence) noted at the hernia repair site will be assessed. If a clinically significant hernia is suspected e.g. bulging noted at the hernia site, it will be confirmed via diagnostic imaging with a CT scan. The occurrence of other post-operative complications (e.g. ileus, bowel obstruction, fistulae) will be also assessed. Disease specific and general Quality of Life (QoL) surveys (HerQLes and EQ-5D), a pain scale and a subject/surgeon satisfaction assessment will also be administered.

At post-operative months 12 and 24, late surgical site occurrences or wound related events (e.g. infections, hematomas, seromas, wound dehiscence, bulging) noted at the hernia repair site will be assessed. If a clinically significant hernia is suspected e.g. bulging noted at the hernia site, it will be confirmed via diagnostic imaging with a CT scan. The occurrence of other late post-operative complications (e.g. ileus, bowel obstruction, fistulae) will also be assessed. Disease specific and general Quality of Life (QoL) surveys (HerQLes and EQ-5D), a pain scale and a subject/surgeon satisfaction assessment will also be administered.

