It is hypothesized that the use of OviTex® Permanent 1S reinforced bioscaffold in abdominal hernia repair (in comparable subjects) will result in less seroma formation, the same percentage or fewer infections and fewer surgical repair related secondary procedures such as fluid aspirations or wound debridement. In addition, the use of OviTex® Permanent 1S reinforced bioscaffold is expected to result in a similar or lower rate of true recurrent herniations as reported for comparable prospectively studied subjects in the literature treated with other implants. [30-33] Surgical procedure related outcomes tend to occur within the first three months after surgery, and the recurrence of a hernia may occur at any point in time after treatment. This study focuses on the surgical outcomes over the first 3 months and continues for a total of 24 months to capture the longer-term incidence of hernia recurrences.

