6.3 ANTICIPATED AND UNANTICIPATED ADVERSE DEVICE EFFECTS

6.3.1 Anticipated Adverse Events

Anticipated adverse events related to ventral hernia repair include post- operative surgical site events such as ileus, deep or superficial wound infection, seroma, hematoma, wound dehiscence, skin necrosis, fistulae and recurrent hernia. A comprehensive list of these events can be found in a patient information brochure at the American College of surgery website; (http://www.facs.org/public info/operation/brochures/ventral hernia.pdf), see Appendix Although anticipated, should these events occur in subjects enrolled in this study, they are considered Adverse Events and should be noted in the eCRF.

In addition to those events listed above, there are other anticipated adverse device effects that include failure of the product to incorporate, rupture of the OviTex® Permanent 1S reinforced bioscaffold sheet or dehiscence of the product, mesh infection, bowel obstructions from adhesions or other mesh complications. These events, although possible and therefore defined as anticipated, are considered to be rare occurrences.

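### Table 1 lets a treated wound event that leaves daily activities unaffected be graded both Mild and Severe, with no rule for which grade prevails

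*Combined protocol and SAP*

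**What the plan says.** Section 6 gives the grading to the site: "The Investigator will assess each event in terms of severity and relationship to study product". Table 1 then defines three grades.

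- **Mild:** "Experiences that are transient, requiring no special treatment, or do not interfere with the" subject's daily activities.
- **Moderate:** some inconvenience or concern, possibly some interference with activities, but "usually ameliorated by simple therapeutic measures, such as over the counter (OTC) medications".
- **Severe:** unacceptable or intolerable, or a significant interruption of usual activity, "and/or require systemic drug therapy or other treatment, including other medical or surgical intervention or hospitalization".

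Section 6.3.1 lists the anticipated events: "ileus, deep or superficial wound infection, seroma, hematoma, wound dehiscence, skin necrosis, fistulae and recurrent hernia". Section 1.2 foresees secondary procedures "such as fluid aspirations or wound debridement". The Study Overview says complications during the hospital stay are assessed, "including the nature and severity of the complications, all necessary medical interventions and/or re-operations". Section 2.3 allows up to 7 sites.

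**The concern.** The two outer grades are defined on different axes, and each can be met on one axis alone. The last Mild condition follows 'or', so an event that does not interfere with activities is Mild whatever treatment it needed. The Severe treatment condition follows 'and/or', so an event that needed systemic drugs or another intervention is Severe however little it disturbed the subject. The conflict is between the ends of the scale, not between neighbouring grades, and it falls on the kind of event the study expects to see.

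At stake is the consistency of the AE severity data. Two sites could grade the same event Mild and Severe and both be following the protocol. The study has one arm, so no internal comparator would show that a shift in the Severe share came from grading habit.

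**Working it through.** The plan states no figure on this point, so there is none to reproduce. The check has three parts.

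**1. Logic of the definitions.** Describe an event by four features:
- T: transient (yes/no)
- S: needs special, systemic or procedural treatment (yes/no)
- I: interference with activities (none, some, significant)
- U: unacceptable or intolerable (yes/no)

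This gives 2 × 2 × 3 × 2 = 24 profiles. Severe is coded as U, or I = significant, or S. The profiles that are not Severe have S = no, U = no and I = none or some, for either value of T: 2 × 2 = 4.

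| Reading of Mild | Mild profiles | of these, not Severe | both Mild and Severe |
|---|---|---|---|
| T, or no S, or no interference (literal 'or') | 24 − 4 = 20 | 4 | **16** |
| (T and no S), or no interference (kinder reading) | 8 + 4 = 12 | 3 | **9** |
| T and no S and no interference ('and') | 2 | 1 | **1** |

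The test event is not transient, treated, not interfering and not intolerable. It is both Mild and Severe under the first two readings and only Severe under the third. The one overlap left under 'and' is implausible: an intolerable event that is also transient, untreated and non-interfering. Among profiles not rated intolerable, the overlap is 0. These are counts of logical profiles, not of expected events.

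**2. Search for a tie-break.** Sections 4, 6, 6.1 to 6.5 and 7 contain no highest-grade rule, worked example or central review of severity grades. Section 6.5 covers sponsor review of SAEs and UADEs only. The glossary lists a Medical Events Committee, but no section available gives it a role.

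**3. Possible size.** The documents give no rate for such events, so the number k is assumed. Take n = 100 subjects, at most one such event per subject and no other Severe events. If every site reads the Mild clause, the Severe rate is 0/100; if every site reads the Severe clause, it is k/100. Exact 95% limits are the 0.025 quantile of Beta(k, n − k + 1) and the 0.975 quantile of Beta(k + 1, n − k).

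| Assumed k | Mild clause read | Severe clause read |
|---|---|---|
| 5 | 0% (0 to 3.6%) | 5% (1.6 to 11.3%) |
| 10 | 0% (0 to 3.6%) | 10% (4.9 to 17.6%) |
| 20 | 0% (0 to 3.6%) | 20% (12.7 to 29.2%) |

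Mixed reading habits would give a rate between the two columns.

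**The case against.** The strongest reply is that no planned result is shown to use the grade. This stands. The endpoints in Section 2.2 are incidences, patient-reported outcomes and recurrence, and an infection or seroma counts whatever its grade. Seriousness is defined separately in Section 6.2. The analyses of interest in Section 7.2 include none on severity, and the literature comparison there is of the primary and secondary endpoints. Section 7.2 refers methods to an SAP whose text is not in the document available, so a severity table can be neither assumed nor ruled out.

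Four stronger readings are therefore not supported.

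- *A reader might infer that the primary results are at risk* because the affected events are endpoint events. They are not at risk, for the reason above.
- *A reader might infer a very large swing.* If 20 of 100 subjects had a site event and half of those events were ambiguous, the Severe share among those 20 could move by 10/20 = 50 percentage points. Both inputs are assumptions, and on all 100 subjects the same case moves 10 points.
- *A reader might hold that Moderate and Severe conflict equally,* since an oral over-the-counter drug acts systemically. Moderate names such medication expressly, and the specific wording naturally governs the general one. This overlap is the weaker one and needs only a clarifying phrase.
- *A reader might extend the problem to UADEs,* because Section 6.4.2 mentions severity. Section 6.3.1 gives no Table 1 grade to any anticipated event, so a dependence on the table is not shown.

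It is also fair that treatments and procedures are already recorded under Section 4, so grades can be re-derived once a rule exists. That makes the defect repairable. It does not settle which grade applies now.

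**Conclusion.** The contradiction is real and follows from the current wording: one event can satisfy both Mild and Severe, and nothing decides between them. It survives the kinder reading of the Mild definition. Its reach is the per-event severity grades and any summary made from them. Those grades could, not necessarily would, vary with the clause each site reads.

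The swing of 5, 10 or 20 percentage points rests wholly on assumed counts and on every ambiguous event being read the same way. Calling these events anticipated is supported by Section 6.3.1; calling them common is not, since no rate is given. This is an inexpensive clarification worth making. It is not a threat to the study's main conclusions.

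**What to change.** Make three changes to Table 1 and carry them into the eCRF help text and a note to sites.

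1. Join the Mild conditions with 'and': the event is transient, needs no special treatment and does not interfere with daily activities.
2. State that the highest grade met applies. This also settles the one overlap left under 'and'.
3. State that the over-the-counter measures named under Moderate do not by themselves meet the Severe treatment condition. Without this phrase, the highest-grade rule could push such events into Severe.

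Leave the Severe treatment trigger as it stands. Removing it would recalibrate the scale, which is a different decision from removing the ambiguity.

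One drafting check follows from change 1. A persistent event that is untreated and does not interfere, such as a seroma simply left alone, would no longer be Mild, and it fits Moderate only if it causes some inconvenience or concern. A sentence saying that any event neither Mild nor Severe is Moderate closes that gap.

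The cost is rewording one table, a one-time re-check of AEs already graded against the treatments and procedures recorded under Section 4, and a somewhat higher share graded above Mild. No new data collection is needed.
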